### 11.6 Trial Design

This is an open-label, parallel design study of 12 and 24 weeks of sofosbuvir/velpatasvir. Subjects are initially started on NHS standard of care treatment, and are consented to participate between treatment week 8-12 (of the standard 12 week course). This design is chosen for several reasons:

- To maximise the time between fulfilling entry criteria (i.e. week 2 ≥ 30iu/mL) and consent, to allow subjects time to consider participation
- Given sofosbuvir/velpatasvir is generally well tolerated, early discontinuation is usually due to non-adherence. By recruiting patients after at least 8 weeks, the study is more likely to recruit subjects willing to adhere to extended treatment. The study specifies that subjects have taken at least 90% of prescribed drugs by screening
- Sofosbuvir/velpatasvir is an expensive treatment and in order to prevent wastage of prescribed NHS treatment when subjects commence on the trial, they are recruited only after the final prescription (each prescription is for one bottle of sofosbuvir/velpatasvir which contains 4 weeks of drug) has been dispensed at treatment week 8. Therefore, only subjects randomised to extended treatment will be dispensed with study drugs.

Maximum duration of participation is 16 weeks for Arm A (12 weeks treatment) - 4 weeks of observation during standard of care treatment, 12 weeks of follow-up, and 28 weeks for Arm B (24 week treatment arm) – 16 weeks of study treatment (4 weeks of standard of care treatment plus 12 weeks of additional IMP treatment), 12 weeks of follow-up.

Treatment week 0 is defined as commencement of sofosbuvir/velpatasvir on NHS treatment programme, before enrolment into the study. Subjects can be pre-screened for study eligibility once week 2 virological response becomes available. Patient information sheet can be provided to interested subjects, but they cannot be consented to participate until week 8 of treatment. Screening and randomisation can take place until the end of standard treatment at week 12.

Upon enrolment into the study until treatment week 12, subjects will proceed according to protocol but they will complete drugs prescribed as part of NHS treatment prior to enrolment. This is in order to reduce wastage of high cost drugs. Sites must ensure sufficient time between enrolment and end of 12 weeks treatment, to dispense additional IMP for participants randomised to arm B (24 weeks).

Study visits are as follows:

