#### Arm A (12 weeks of sofosbuvir/velpatasvir)

Screening / baseline (treatment week 8 up to week 12)

Randomisation by coordinating centre

Treatment week 12 (end of study treatment)

Treatment week 16 (post treatment week 4)

Treatment week 20 (post treatment week 8)

Treatment week 24 (post treatment week 12 – study endpoints & end of study)

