Study participants will undergo block randomisation such that at any time during the study, roughly equal numbers will be recruited into both arms, allowing for interim analysis as necessary. An interim analysis may be performed when about 50% of planned recruitment has taken place, to assess safety and efficacy, whether the study sample needs to be altered. This will be determined by the Chief Investigator and/or the Trial Steering Committee.

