#### 19.2 Planned recruitment rate

The study plans to recruit 60 participants from 5 London sites in 9 months. Each site therefore has to recruit 12 patients, at a rate of less than 2 patients per month.

There are estimated 10,000 HCV infected individuals in England who have cirrhosis. Around 45% may be infected with genotype 3. The study target group is enriched within London where there is a high immigrant population (where genotype 3 HCV prodominates) and a concentration of patients with cirrhosis or advanced liver disease, currently over 30% of treated patients nationally have cirrhosis. At Royal London Hospital (one of the study sites), approximately 3 new patients with genotype 3

HCV are identified to start treatment each week. Amongst patients treated within the Expanded Access Programme, around 50% of patients did not achieve undetectable HCV after 2 weeks of treatment. In a phase 3 trial of 12 weeks of sofosbuvir/velpatasvir, which did not include the hardest to treat patients with decompensated cirrhosis, 38% did not achieve undetectable HCV at treatment week 2, and this is expected to be higher for a cohort including decompensated cirrhosis [20].

Sofosbuvir/velpatasvir is due to become routinely available as NHS treatment in the upcoming months. The number of prescriptions for high cost interferon-free therapies for genotype 3 patients is determined by the treatment centre's 'run rate'. Participating sites have indicated that the number of subjects required for recruitment is within their run rate allowance.

Given the entry criteria for the study match the NHS eligibility criteria for sofosbuvir/velpatasvir use, identification of suitable patients for recruitment, using the NHS treatment network, will be straightforward. Chosen study sites are all experienced HCV treatment and clinical trial centres, with a good track record of recruitment for regional and international studies.

Based on the low discontinuation rate on the Expanded Access Programme in England, where real world patients with advanced liver disease were treated [14], the study does not anticipate premature treatment or study withdrawal to be a major problem. The study will recruit patients who adhered to 90% of their treatment at screening, to eliminate the risk of early drop outs.

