#### 19.9 Interim analysis and criteria for the premature termination of the trial

An interim analysis of efficacy and safety will be considered through discussion with the Trial Steering Committee when about half the planned sample size is recruited to evaluate if there is an indication to discontinue the trial, alter the sample size, or replace participants who withdraw.

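### The optional efficacy interim at half of recruitment comes before any Arm B completer can have SVR12, so it cannot compare the arms when it is triggered

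*Protocol*

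**What the plan says.** Section 19.1 of the protocol makes the look optional, ties it to recruitment and gives it an efficacy purpose: "An interim analysis may be performed when about 50% of planned recruitment has taken place, to assess safety and efficacy". It leaves the decision to the Chief Investigator and/or the Trial Steering Committee. Section 19.9 repeats the trigger, at about half of the planned sample, and gives the aim as "to evaluate if there is an indication to discontinue the trial, alter the sample size, or replace participants who withdraw". Sections 13.5.1 and 19.1 both justify block randomisation partly because it would give balanced groups for such an analysis, so a comparison between arms was in view.

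The timing inputs are stated elsewhere in the protocol:

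- Section 19.2 on accrual: "The study plans to recruit 60 participants from 5 London sites in 9 months".
- Section 11.6 on entry: patients already on treatment can join late, since "they cannot be consented to participate until week 8 of treatment", and "Screening and randomisation can take place until the end of standard treatment at week 12".
- The Arm A visit list in section 11.6 places the primary endpoint at "Treatment week 24 (post treatment week 12 – study endpoints & end of study". The Arm B list places it at treatment week 36.
- Section 19.11 counts a negative HCV RNA before 12 weeks post-treatment as non-SVR12 and does not allow results outside the window to be carried forward.

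**The concern.** An interim look at efficacy needs primary outcomes from both arms. Balance in the number randomised does not give balance in the number with outcomes, because Arm B reaches its endpoint 12 weeks later than Arm A. If the trigger falls before Arm B can contribute, the look cannot do what sections 19.1 and 13.5.1 want from it. A decision to stop or resize the trial on efficacy grounds would then depend on how a handful of control-arm patients had done against the assumed 65%, with nothing known about the extended arm.

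**Working it through.** **Reproducing the plan's own durations.** Time from enrolment to endpoint is the endpoint week minus the enrolment week, and enrolment is at treatment week 8 to 12.

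- Arm A: 24 − 12 = 12 weeks to 24 − 8 = 16 weeks. Section 11.6 agrees: "Maximum duration of participation is 16 weeks for Arm A".
- Arm B: 36 − 12 = 24 weeks to 36 − 8 = 28 weeks. Section 11.6 gives 28 weeks as the Arm B maximum.

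The endpoint window of +4 weeks can only lengthen these times.

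**When the look falls.** Nine months is 9 × 365.25 / 12 / 7 = 39.1 weeks. With uniform accrual (an assumption, as the protocol gives only the total), 30 of 60 are recruited at 39.1 / 2 = 19.6 weeks, or 4.5 months.

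**Results available at the look.** With 1:1 allocation, 30 per arm accrue over 39.1 weeks. The number with SVR12 at time t is (t − lag) / 39.1 × 30, or zero if the lag exceeds t.

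| | Enrolled at week 8 | Enrolled at week 12 |
|---|---|---|
| Arm A | (19.6 − 16) / 39.1 × 30 = 2.7 | (19.6 − 12) / 39.1 × 30 = 5.8 |
| Arm B completers | 19.6 < 28, so 0 | 19.6 < 24, so 0 |

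So there are about 3 to 6 Arm A results and no Arm B completers.

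**How slow recruitment would have to be.** The first Arm B completer has a result at the half-way point only if half the recruitment period is at least 24 to 28 weeks. Recruitment would have to last 48 to 56 weeks, or about 11.0 to 12.9 months, against a plan of 9.

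**What happens if the look is deferred.**

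- First Arm B completer evaluable: 24 to 28 weeks, or 5.5 to 6.4 months, with about 37 to 43 of 60 recruited.
- Evaluable at month 9: Arm B (39.1 − 28) / 39.1 × 30 = 8.5 to (39.1 − 24) / 39.1 × 30 = 11.6. Arm A (39.1 − 16) / 39.1 × 30 = 17.7 to (39.1 − 12) / 39.1 × 30 = 20.8.
- All of the first 30 evaluable: 19.6 + 24 = 43.6 to 19.6 + 28 = 47.6 weeks, or 10.0 to 10.9 months (10.9 to 11.9 months if the full +4 week window is used).

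**Type I error, for a hypothetical look with outcomes in both arms.** Take two two-sided tests, at half and at full information, with correlation √0.5.

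- Both at an unadjusted 5%: overall error 8.3%. Exact enumeration of the chi-square test (15 then 30 per arm) gives 8.3% at a common SVR of 65%, 8.3% at 80% and 3.1% at 95%.
- Haybittle-Peto (p<0.001 at the interim, 0.05 at the end): overall error 5.0%.
- At 15 per arm and the planned 65% against 95%, exact enumeration gives about a 6% chance that a chi-square test crosses p<0.001.

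**The case against.** The look is optional, the sponsor can choose not to hold it, and its safety and withdrawal purposes work at the stated time. Nine months is a plan: section 11.7 foresees a recruitment review at around month 6 and possible extra sites, and section 13.9 allows withdrawn participants to be replaced if the sample is judged underpowered. Boundaries are commonly left to an analysis plan or a committee charter. All of this stands, and it limits the point to the trigger. An analysis plan could add a boundary, but it could not supply Arm B outcomes at half of recruitment.

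Four stronger readings are tempting and not supported:

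- *No Arm B participant could have a result.* Section 13.9 lets those who stop treatment stay in follow-up, so someone who stopped soon after week 12 could have a result 12 to 16 weeks after enrolment. The statement is true of completers at the planned pace. The exception does not rescue the look, because those results come from people who did not receive 24 weeks.
- *Any workable efficacy look falls after recruitment ends.* That is true only if SVR12 is required on all of the first 30. A smaller look at both arms fits before month 9.
- *The plan inflates type I error to 8.3%.* The protocol states no interim test or level and does not say that the look is unadjusted. A look without Arm B outcomes also spends no alpha on the comparison.
- *The protocol provides for stopping on efficacy.* Section 19.9 does not give the ground for discontinuing. The termination authority in section 28.0 concerns unacceptable risk to patients.

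**Conclusion.** The concern holds as a fault in the trigger. At 60 participants in 9 months with uniform accrual, the half-recruitment look has about 3 to 6 Arm A results and none from Arm B completers, so its stated efficacy purpose cannot be met. This survives any recruitment period shorter than about 11 months, and up to about 12.9 months if patients enrol at treatment week 8. Any efficacy-based decision at that point would rest on control-arm data. The type I error figure is conditional: it describes a different look, with outcomes in both arms and two unadjusted 5% tests. This should be changed, but because the look is optional and its safety role is sound, it does not undermine the trial.

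**What to change.** In sections 19.1 and 19.9, limit the half-recruitment look to safety, recruitment, withdrawals and completeness of follow-up. State that it includes no efficacy comparison and no efficacy-based change of sample size.

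If an efficacy look is wanted, trigger it on a stated number of SVR12 results in each arm and state a stringent boundary, for example Haybittle-Peto with p<0.001 at the interim and 0.05 at the end. Record that at about 15 per arm this boundary would rarely be crossed even under the planned effect, and that SVR12 on all of the first 30 arrives after the planned end of recruitment.

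The cost is a change of wording. It gives up an optional efficacy look that could not work as timed.

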#### 19.2 Planned recruitment rate

The study plans to recruit 60 participants from 5 London sites in 9 months. Each site therefore has to recruit 12 patients, at a rate of less than 2 patients per month.

There are estimated 10,000 HCV infected individuals in England who have cirrhosis. Around 45% may be infected with genotype 3. The study target group is enriched within London where there is a high immigrant population (where genotype 3 HCV prodominates) and a concentration of patients with cirrhosis or advanced liver disease, currently over 30% of treated patients nationally have cirrhosis. At Royal London Hospital (one of the study sites), approximately 3 new patients with genotype 3

HCV are identified to start treatment each week. Amongst patients treated within the Expanded Access Programme, around 50% of patients did not achieve undetectable HCV after 2 weeks of treatment. In a phase 3 trial of 12 weeks of sofosbuvir/velpatasvir, which did not include the hardest to treat patients with decompensated cirrhosis, 38% did not achieve undetectable HCV at treatment week 2, and this is expected to be higher for a cohort including decompensated cirrhosis [20].

Sofosbuvir/velpatasvir is due to become routinely available as NHS treatment in the upcoming months. The number of prescriptions for high cost interferon-free therapies for genotype 3 patients is determined by the treatment centre's 'run rate'. Participating sites have indicated that the number of subjects required for recruitment is within their run rate allowance.

Given the entry criteria for the study match the NHS eligibility criteria for sofosbuvir/velpatasvir use, identification of suitable patients for recruitment, using the NHS treatment network, will be straightforward. Chosen study sites are all experienced HCV treatment and clinical trial centres, with a good track record of recruitment for regional and international studies.

Based on the low discontinuation rate on the Expanded Access Programme in England, where real world patients with advanced liver disease were treated [14], the study does not anticipate premature treatment or study withdrawal to be a major problem. The study will recruit patients who adhered to 90% of their treatment at screening, to eliminate the risk of early drop outs.

Currently there are no competing clinical trials for the study population but this may change throughout the duration of the trial. However most clinical trials will involve experimental IMPs while this study uses treatment which patients have already consented to start. The study and treatment schedule requirements are similar to that within routine NHS treatment, therefore we anticipate the study will be considered favourably by patients.

#### 19.3 Statistical analysis plan (SAP)

All statistical analysis will be performed as specified *a priori* on the whole study population (intention to treat), with post-hoc analysis performed as appropriate. These are detailed below.

# 19.4 Summary of baseline data and flow of patients

Demographic and baseline characteristics will be summarised using standard descriptive methods. Data will include gender, self-identified ethnicity, age, previous treatment experience, body mass index, baseline (pre-treatment) HCV RNA level, week 2 HCV RNA level, genotype of HCV infection, baseline laboratory values (haemoglobin, platelet count, creatinine, ALT, bilirubin, albumin) and liver severity score (MELD score) generated from the above baseline laboratory values.

Categorical data will be summarised by proportions and continuous data summarised by mean, median and range.

Flow of patients will be reported according to CONSORT guidelines.

# 19.5 Primary outcome analysis

The proportion of patients receiving 12 and 24 weeks of sofosbuvir/velpatasvir with undetectable HCV RNA (below limit of quantification up to 15iu/mL) in serum at 12 weeks (+4 weeks) after end of treatment (sustained virological response SVR12).

SVR12 will be calculated on intention to treat, i.e. all randomised participants who received at least one dose of study drug will be included. Patients randomised will have completed at least 90% of sofosbuvir/velpatasvir at screening (between treatment week 8-12). Patients randomised to 24 weeks must have taken at least one dose of the extension phase treatment. Comparison of proportions will be analysed by Chi-square test.

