## 10.0 Trial Flowchart

## 11.0 Trial Objectives and Design

## 11.1 Primary Objective/s

To compare the efficacy (the proportion of randomised patients who achieve a sustained virological response – defined as undetectable HCV RNA (below limit of quantification up to 15 iu/mL) at 12 weeks (up to 16 weeks) after end of treatment – SVR12) of 12 OR 24 weeks of sofosbuvir/velpatasvir in patients with genotype 3 chronic HCV and cirrhosis, who have detectable viraemia (≥ 30 iu/mL) at week 2 (+/- 3 days) of treatment with sofosbuvir/velpatasvir.

Patients randomised must have completed at least 90% of sofosbuvir/velpatasvir at screening, and patients randomised to 24 weeks must have taken at least one dose of the extension phase treatment.

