# 19.0 Statistical and Data Analysis

#### 19.1 Sample size calculation

The planned sample size is 60 participants - with 30 participants in each of two treatment arms. This is based on the assumption of a 30% difference in the primary outcome measure (proportion of patients who achieve SVR12) between the two treatment arms, where SVR in the 12 week treatment arm is 65%, and 95% in the 24 week treatment arm. All outcomes are measured on an intention to treat basis.

Estimates of SVR rates for patients with slow treatment response (week 2 HCV detectable) is derived from post-hoc analyses of cohort studies or clinical trials. For genotype 3 patients with decompensated cirrhosis treated with sofosbuvir and NS5A inhibitor (daclatasvir or ledipasvir) with or without ribavirin, SVR was 65% for patients viraemic at week 2 [14]. There is no data available for this subgroup treated with sofosbuvir/velpatasvir. For all genotype 3 patients with decompensated cirrhosis, SVR was 50% after 12 weeks of sofosbuvir/velpatasvir [16], and 91% for patients with compensated cirrhosis [15]. Another study showed that a combination of 3 negative factors in genotype 3 patients dropped SVR after 12 weeks of sofosbuvir/velpatasvir to 85%, from 95% if only 2 negative factors were present [18].

Given the trial cohort will contain compensated and decompensated patients, the SVR after 12 weeks is estimated at 65%. The study assumes an SVR of 95% with the extended arm, in order for the margin of improvement to be clinically and statistically significant, as well as cost-effective to justify the increased drug costs. This is a realistic assumption given 12 weeks of sofosbuvir/velpatasvir in genotype 3 patients without negative factors (i.e. without cirrhosis) achieved SVR of 97% [15]. This study will demonstrate if treatment extension can overcome the impact of negative treatment factors on SVR.

To detect a true difference between the two treatment arms (if one exists) with 80% power and 95% confidence level, 24 participants are required as a minimum in each arm. The study will recruit 60 participants to allow for withdrawals or those lost to follow up.

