# 19.10 Subject population

All data will be reported on an intention to treat basis such that all randomised participants who received one dose of study drug will be included (entry criteria dictates all participants have adhered to 90% of treatment at the point of screening). Per protocol analysis will be analysed and reported as appropriate, for instance if there is an unexpectedly high treatment discontinuation or lost to follow up rate. For per protocol analysis, participants who adhered to 90% of their treatment according to randomisation will be included.

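### The primary set is called intention to treat but requires an extension dose in Arm B only, which can bias the comparison towards 24 weeks

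*Protocol*

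**What the plan says.** All references are to the protocol.

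- Section 19.5 describes the primary analysis as intention to treat and defines it so that "all randomised participants who received at least one dose of study drug will be included". Section 19.10 repeats the rule: "all randomised participants who received one dose of study drug will be included".
- Section 11.1 adds, inside the primary objective, that "patients randomised to 24 weeks must have taken at least one dose of the extension phase treatment". Section 19.5 repeats this condition. No condition after randomisation is set for Arm A. The 90% adherence rule is met at screening and applies to both arms.
- Section 11.1 also defines efficacy as a proportion of those randomised, and section 19.3 promises analysis of the whole study population by intention to treat.
- Section 13.5.1 places randomisation between treatment weeks 8 and 12. Until the end of week 12 both arms take the same NHS-supplied drug. Section 11.6 states that "only subjects randomised to extended treatment will be dispensed with study drugs", and section 15.1 limits study drug to weeks 13 to 24.
- Section 19.11 treats loss to follow-up as one form of non-SVR12 and does not allow results from outside the 12 to 16 week window to be carried into it.

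**The concern.** Starting the extension happens after randomisation and can happen in one arm only. In this open-label trial, a participant may stop, die, be lost, or decline the extension between randomisation and week 13. In Arm B that person leaves the denominator. In Arm A the comparable person stays in it and, without an HCV RNA result in the window, counts as non-SVR12. The two groups compared are then no longer the two groups randomised, although the set is labelled intention to treat.

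The direction matters. Where early leavers do worse than those who stay, the exclusion removes failures from the experimental arm alone. Section 15.2 says NHS England would adopt the 24-week regimen if this trial supports it, so a primary comparison that can lean towards 24 weeks bears directly on the decision.

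**Working it through.** **Inputs from the protocol.** Section 19.1: "SVR in the 12 week treatment arm is 65%, and 95% in the 24 week treatment arm"; "with 80% power and 95% confidence level, 24 participants are required as a minimum in each arm"; "The planned sample size is 60 participants - with 30 participants in each of two treatment arms"; "The study will recruit 60 participants to allow for withdrawals or those lost to follow up". Section 19.5: chi-square test. I take the 95% confidence level to mean a two-sided 5% test.

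**The plan's own figure.** With the unpooled two-proportion formula,

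n = (1.960 + 0.842)² × (0.65×0.35 + 0.95×0.05) / 0.30² = 7.849 × 0.275 / 0.09 = 23.98, so 24 per arm.

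The stated minimum is reproduced. Going from 24 to 30 per arm allows for 6 losses in each arm (6/30 = 20%).

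**Assumptions not in the protocol.** k is the number of participants per arm who leave between randomisation and week 13. No value is given, so I use k = 1 to 6, the upper end being the section 19.1 allowance. For the null case I set the true SVR at 65% in both arms among those who stay.

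**Expected bias under the null.** Let q be the SVR of early leavers as counted in Arm A, with no result meaning q = 0.

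- Arm A expected SVR = [(30 − k) × 0.65 + k × q] / 30
- Arm B expected SVR under the written rule = 0.65, because the k leavers are dropped
- Spurious difference = k × (0.65 − q) / 30

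This is zero if q = 0.65 and largest if q = 0.

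**Worst case, q = 0.** The chance of a significant result is an exact sum over all binomial outcomes, using the uncorrected chi-square test. Under the written rule, Arm A has n = 30 with k fixed failures and Arm B has n = 30 − k. Under the all-randomised rule, both arms have n = 30 with k fixed failures.

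| k | Arm A expected | Arm B, written rule | Spurious difference | Significant for 24 weeks, written rule | Same, all randomised |
|---|---|---|---|---|---|
| 0 | 65.0% | 65% | 0 | 2.4% | 2.4% |
| 1 | 62.8% | 65% | +2.2 points | 3.8% | 2.1% |
| 2 | 60.7% | 65% | +4.3 points | 5.2% | 1.8% |
| 3 | 58.5% | 65% | +6.5 points | 6.6% | 1.6% |
| 6 | 52.0% | 65% | +13.0 points | 14.7% | 1.1% |

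The nominal rate in this direction is 2.5%.

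**Mild case, q = 0.65.** Arm B non-starters complete 12 weeks and reach 65%, and their Arm A counterparts do the same. The expected difference is 0, and the chance of a significant result for 24 weeks is 2.6%, 2.7%, 2.5% and 2.7% for k = 1, 2, 3 and 6. There is no material inflation.

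**If the planned effect is real (65% against 95%).**

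- Mild case: dropping the non-starters puts Arm B at 95%. Keeping all randomised gives (29×0.95 + 1×0.65)/30 = 94% for k = 1, and 92% and 89% for k = 3 and 6.
- Worst case: the expected difference under the written rule is 32.2, 36.5 and 43.0 points for k = 1, 3 and 6, against 29.0, 27.0 and 24.0 with all randomised.

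**The case against.** The strongest reply is that the bias is conditional and probably small. Sections 13.8.4, 13.9 and 13.10 let participants who stop treatment stay in follow-up, and seek consent to collect SVR12 from those who withdraw. By randomisation every participant has had at least 8 weeks of treatment with at least 90% adherence, so an early leaver may still be cured. A likely Arm B non-starter is someone who completes 12 weeks and then declines the extension. The Arm A counterpart simply counts by the actual result, which is the mild case above. Section 19.2 expects few withdrawals, and the window is about four weeks at most. All of this stands. It limits the size of the problem but does not justify a condition that applies to one arm.

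A reader might go further in three ways that the protocol does not support.

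- That every Arm A early leaver is a failure. Section 19.11 makes this certain only where there is no HCV RNA result in the 12 to 16 week window.
- That the one-dose rule empties Arm A, because only Arm B is dispensed study drug. Section 15.2 treats both durations as investigational product and section 11.6 calls Arm A's week 12 the end of study treatment. This is loose terminology, not an intended exclusion.
- That open allocation will be used to exclude failures selectively. Open allocation gives the opportunity and no more, and the endpoint is a laboratory result.

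**Conclusion.** The definition is wrong as written. It imposes a post-randomisation condition on Arm B alone, calls the result intention to treat, and conflicts with sections 11.1 and 19.3. Nothing else in the protocol repairs it.

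It can bias the primary comparison towards 24 weeks, but it does not necessarily do so. Bias under the null needs early leavers who lack an SVR12 result or have a lower SVR than those who stay. If their results are collected and are no worse, there is no null bias, but a real Arm B benefit would still be overstated relative to all randomised.

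The table gives the upper end, where every early leaver lacks a result. With one to three per arm, the spurious difference is 2.2 to 6.5 points and the one-directional error is 3.8% to 6.6%, against 2.4% with none. The 14.7% at six per arm needs the whole withdrawal allowance to fall in this short window. These figures rest on the assumed k and on 65% SVR in both arms. The case for correcting the rule does not depend on them.

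**What to change.** 1. In sections 11.1, 19.5 and 19.10, define the primary set as all randomised participants, analysed in the arm assigned, whether or not an extension dose was taken.
2. Use SVR12 results collected after stopping or withdrawal where they exist, and count missing SVR12 as non-SVR12 in both arms.
3. Delete the extension-dose condition from the primary objective and the primary analysis. Keep that set for Arm B tolerability, where section 19.6 already gives a good reason for it, and as a labelled sensitivity analysis.
4. Replace the wording about one dose of study drug, because sections 15.1 and 15.2 use the term differently.

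This is a wording change in three sections and needs no data beyond what section 13.9 already seeks. The observed Arm B SVR may be slightly lower. Power also falls if early leavers lack results: for 65% against 95% among those who stay, with all 30 per arm kept, exact power is 88% at k = 0, 82% at k = 1, 76% at k = 2 and 70% at k = 3. Collecting outcomes from those who stop limits that loss.

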#### 13.5 Patient Allocation

#### 13.5.1 Randomisation Method

Participants who fulfill inclusion/ exclusion criteria will be randomised. This takes place anytime after enrolment between treatment week 8 to 12. Sites must ensure sufficient time to randomise participants and dispense additional IMP for those in the arm B (24 weeks) such that there will not be more than 24 hours before commencing week 13 treatment.

Participants will be allocated into treatment arms A and B in a 1:1 ratio, by block randomisation, and stratified by whether they have compensated cirrhosis or decompensated cirrhosis at baseline. Participants with previous history of decompensation will be considered as having decompensated cirrhosis for the purpose of stratification. This is in order to generate equal numbers within each arm, with balanced severity of liver disease distributed. Clinical trial data suggests that severity of liver disease and presence of decompensated cirrhosis are one of the most important factors determining treatment outcome [8].

There may be other patient factors which influence treatment success, but further stratification for a study of 60 participants would not be appropriate. Block randomisation will enable interim analysis to be performed with balanced groups.

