#### 19.8 Adjusted analysis

Adjusted analysis or other post-hoc analysis will be performed as appropriate.

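### Randomisation is stratified by decompensation but the primary chi-square test is not: valid, mildly conservative, and improvable at no cost

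*Protocol*

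**What the plan says.** Protocol section 13.5.1 plans equal allocation to the two arms in blocks, with the randomisation "stratified by whether they have compensated cirrhosis or decompensated cirrhosis at baseline". Its reason is that "severity of liver disease and presence of decompensated cirrhosis are one of the most important factors determining treatment outcome".

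Section 19.5 compares the arms on SVR12 with one sentence: "Comparison of proportions will be analysed by Chi-square test". It names no stratum or covariate. Decompensation returns in section 19.7 as a subgroup. Section 19.8 says only that "Adjusted analysis or other post-hoc analysis will be performed as appropriate".

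Section 19.1 plans for a comparison "where SVR in the 12 week treatment arm is 65%, and 95% in the 24 week treatment arm", and states that "with 80% power and 95% confidence level, 24 participants are required as a minimum in each arm". It adds that "The study will recruit 60 participants to allow for withdrawals or those lost to follow up". The same section gives 12-week SVR in genotype 3 patients as 50% with decompensated cirrhosis and 91% with compensated cirrhosis.

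**The concern.** Stratified blocks balance decompensation between the arms, so differences between strata contribute almost nothing to the random variation of the arm difference. The plain chi-square takes its variance from the pooled SVR proportion, which still contains that between-stratum variation. If the factor is prognostic, the assumed variance is too large, the real type I error falls below the nominal 5%, and some power is lost.

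The protocol itself calls the factor one of the most important for outcome. Section 19.3 presents the analyses that follow it as specified a priori, and section 19.5 names the test. The choice is therefore made in the protocol and is not merely left for an analysis plan to settle. What is at stake is efficiency in a 60-patient trial. There is no added risk of a false positive.

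**Working it through.** **Inputs from the protocol.** 1:1 allocation, two strata, 30 per arm planned and 24 per arm minimum; SVR12 65% versus 95%; 80% power; 95% confidence, read as two-sided alpha 0.05; 12-week rates of 50% and 91% by stratum (a 41-point gap).

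**Assumptions.** The protocol does not give the decompensated share; I vary it from 20% to 63%. The upper end is the mix at which 50% and 91% average to 65%: (0.91 − 0.65)/(0.91 − 0.50) = 0.634, or about 19 of 30 per arm. The gap in the trial population is also unknown; I use 41, 20 and 0 points. Arms are taken as equal within strata.

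**Step 1: the protocol's own figure.** The unpooled two-proportion formula gives n = (1.96 + 0.8416)² × (0.65×0.35 + 0.95×0.05)/0.30² = 23.98, so 24 per arm, as stated. With no difference between strata, exact power of the uncorrected chi-square is 0.808 at 24 per arm and 0.880 at 30.

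**Step 2: why it is conservative.** Take 19 decompensated and 11 compensated per arm, with the 50% and 91% rates in both arms.
- Mean within-stratum variance: (19/30)×0.25 + (11/30)×0.0819 = 0.188.
- Pooled variance: 0.650×0.350 = 0.227.
- Ratio: 0.828.
- Approximate true size: 2×[1 − Φ(1.96/√0.828)] = 0.031.

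Exact enumeration of all outcomes gives 0.029 for the chi-square and 0.050 for the Cochran-Mantel-Haenszel (CMH) test.

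**Step 3: type I error at 30 per arm**, exact, no continuity correction, overall rate 65%, decompensated share 20% to 63%:

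| Gap between strata | Chi-square | CMH |
|---|---|---|
| 41 points | 0.028 to 0.034 | 0.050 |
| 20 points | 0.043 to 0.045 | 0.048 to 0.049 |
| none | 0.048 | 0.048 to 0.049 |

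**Step 4: power at 30 per arm, 65% versus 95% overall.**
- 41-point gap: CMH gains 0.8 to 2.1 points. With 19 decompensated per arm it is 0.892 versus 0.908 under a common odds ratio, and 0.891 versus 0.899 if both strata reach 95%.
- 20-point gap: 0.2 to 0.7 points.
- No gap: at most 0.2 points.

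**Step 5: power if the 24-week rate is lower.** 41-point gap, 30 per arm, common odds ratio, 10 to 19 decompensated per arm:

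| 24-week rate | Chi-square | CMH |
|---|---|---|
| 80% | 0.234 to 0.236 | 0.280 to 0.286 |
| 85% | 0.428 to 0.430 | 0.477 to 0.488 |
| 90% | 0.668 to 0.671 | 0.709 to 0.720 |

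The gain is about 4 to 6 points. With a 20-point gap (55% and 75%, equal strata) it is about 1.5 points at each of these rates.

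**Step 6: continuity correction.** At 30 per arm and 65% versus 95%, a continuity-corrected CMH test has power of only 0.79 to 0.83, below the uncorrected chi-square's 0.88 to 0.89.

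**The case against.** The strongest case against acting has four parts.

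- **The loss is small at the design effect.** With 65% versus 95% it is at most about 2 points. Small-sample discreteness can even reverse it: with 27 per arm (17 decompensated), the 50% and 91% rates and both strata reaching 95%, the chi-square has 0.868 and CMH 0.864. This stands.
- **The 41-point gap is not for this population.** The 50% and 91% are for all genotype 3 patients, while the trial enrols only those still viraemic at week 2. Section 9.1 says that the decompensated figures come from groups of 12 to 14 patients. Section 19.1 says that no data exist for slow responders on this combination, and its slow-responder figure for decompensated patients on other combinations is 65%, the same as the planned overall rate. This also stands, and is why a range is needed.
- **The error is in the safe direction.** The chi-square matches the two-proportion sample size. Section 13.5.1 gives balance as the aim of stratifying, and balance is achieved whichever test is used. This stands too.
- **An unseen analysis plan may settle it.** This does not stand. Section 19.5 already names the test, so a stratified primary analysis elsewhere would contradict it.

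A reader might infer that the primary test is invalid, that the trial is underpowered, or that stratifying has been wasted. The documents do not support any of these: type I error is not inflated, 24 per arm reproduces, and power at 30 per arm is about 0.88 to 0.89 with the planned test. Larger power gains can be produced only with stratum rates that the protocol does not give or with effects smaller than it plans for.

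**Conclusion.** The mismatch between design and analysis is real but minor. The planned chi-square controls type I error and is conservative to a degree that depends on how far SVR differs between the strata. That gap and the stratum mix are assumptions, so the result is a range. At worst, with the full 41-point gap, the test runs at roughly 3% in place of 5%; with no gap the two tests are practically equivalent. The planned sample size is not undermined. The best reason to change is that the 95% assumed for 24 weeks may prove optimistic: a stratified test helps most when the true effect is smaller and the strata differ widely. Naming it in advance also removes the choice between adjusted and unadjusted results that section 19.8 leaves open.

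**What to change.** In section 19.5, replace the sentence naming the chi-square test. Specify as primary a Cochran-Mantel-Haenszel test without continuity correction, stratified by compensated versus decompensated cirrhosis as used at randomisation. Report the Mantel-Haenszel stratum-weighted difference in SVR12 with its 95% CI. Keep the unstratified chi-square as a sensitivity analysis. State the absence of a continuity correction explicitly, because a corrected version would cost more power than stratifying gains.

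The cost is a short edit to one section. The factor is already recorded at randomisation, and no extra data or participants are needed.
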